## 7.5. Statistical models

### 7.5.1. Fixed effect Poisson regression model

#### 7.5.1.1. Rationale

Analysis of risk factors for incident endpoints will be done using the person-time method described above.

The effect of the covariates on the outcomes of interest will be evaluated based on the relative incidence rates (incidence rate ratios) obtained by means of Poisson regressions.

Both univariate and multivariable Poisson regression models will be used. Incidence rate ratio will be the measure of association used to estimate the relative risk of the outcome due to covariates.

#### 7.5.1.2. Method

The Poisson regression model expresses the natural logarithm of the event or outcome of interest as a linear function of a set of predictors. The dependent variable is the number of events ( $Y$ ). The model will include the covariates  $X_1 \dots X_n$ , the study site [Z] as a fixed effect, and the log-transformed total person-time ( $PY$ ).

Main model:  $\ln(Y) = \beta_0 + \beta_1 X_1 + \dots + \beta_n X_n + \beta_Z Z + \ln(PY)$

The coefficients  $\beta_1 \dots \beta_n$  and  $\beta_Z$  are the coefficients associated to covariates  $X_1 \dots X_n$  and study sites, respectively. The risk ratio will be derived as the exponential of the coefficient associated with the covariate status and its 95% Wald CI.

Poisson regression will be conducted using the SAS GENMOD procedure:

```
PROC GENMOD data=<filename> ;  
  CLASS X1 [...] Xn Z;  
  MODEL Y= X1 [...] Xn Z / OFFSET=Ln_PY DIST=poisson LINK=log ;  
  RUN;
```

For each model, the following assumptions will be checked in order to interpret the results obtained from the Poisson regression: the outcome variable follows a Poisson distribution and does not have an excessive number of zeros. The deviance will measure the adequacy of the model. If the scaled deviance is closed to one, the regression model is adequate. Otherwise, the validity of the model is questionable. In particular, value greater than 1 indicates overdispersion.

In case of overdispersion, corrective measures will include the introduction of a dispersion parameter with respect to the Poisson model. This will be done by adding the option DSSCALE and examining the fit statistics. If overdispersion is still a problem, another alternative approach considering a negative binomial distribution model will be discussed considering scientific inputs.

Of note, the same procedure PROC GENMOD will be adapted by specifying option DIST=negbin in the model statement:

```
PROC GENMOD data=<filename> ;  
  CLASS X1 [...] Xn Z;  
  MODEL Y= X1 ... Xn Z / OFFSET=Ln_PY DIST=negbin LINK=log ;  
  RUN;
```

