9.7.8. Statistical considerations

All the statistical calculations will be done in SAS 9.2 or higher.

Unless specified otherwise, all the statistical tests will be two-sided at alpha level of 0.05.

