9.7.9. Statistical models

Poisson regression will be conducted using the SAS GENMOD procedure. The dependent variable is the number of events (Y). The model will include the study site as a fixed effect, the log-transformed total person-time (PY) as an offset and the risk factors.

Main model: $\ln(Y) = \beta_0 + \beta_1 X_1 + \dots + \beta_k X_k + \ln(PY)$

The coefficients β_1 and β_i are the coefficients associated to study sites and the covariates, respectively. The risk ratio of covariates will be derived as the exponential of their associated coefficient and their 95% Wald CI.

The SAS code is:

```
PROC GENMOD data=<filename> ;
  CLASS X1 Xk;
  MODEL Y= X1 Xk / OFFSET=Ln_PY DIST=poisson LINK=log ;
  RUN;
```

For each model, the following assumptions will be checked in order to interpret the results obtained from the Poisson regression: the outcome variable follows a Poisson distribution and does not have an excessive number of zeros. The deviance will measure the adequacy of the model. If the scaled deviance is closed to one, the regression model is adequate. Otherwise, the validity of the model is questionable. In particular, value greater than 1 indicates over dispersion.

In case of over dispersion, corrective measures will include the introduction of a dispersion parameter with respect to the Poisson model. This will be done by adding the option DSSCALE and examining the fit statistics. If over dispersion is still a problem, another alternative approach considering a negative binomial distribution model will be discussed considering scientific inputs.

CONFIDENTIAL115055 (EPI-MALARIA-002 VS AME)
Protocol Amendment 7 Final

This last method will be detailed further in the SAP. Of note, the same procedure PROC GENMOD will be adapted by specifying option DIST=negbin in the model statement:

```
PROC GENMOD data=<filename> ;
  CLASS X1 Xk;
  MODEL Y= X1 Xk / OFFSET=Ln_PY DIST=negbin LINK=log ;
  RUN;
```

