### 6.11.2. Derivation of incidence rate and prevalence

- For all endpoints listed in **Table 4** incidence rate will be calculated by dividing the number of all cases over the follow-up period by person-year as defined in the table.

If a subject had several cases during the period defined, all episodes will be reported.

The number of person-years will be computed as the sum of subjects follow-up period expressed in years.

**Table 3** Follow-up period definition for other secondary endpoints

Analysis	Start	Stop (earliest)
D3 → D3 + 1Y	Third dose or virtual vaccination*	
 
• One year after third dose
 
• Date of death
 
• Date of last contact**
 
• Date of migration
 
• Date when child reaches 5 years
 

D3 → D4 + 1Y	Third dose or virtual vaccination*	
 
• One year after virtual fourth dose
 
• Date of death
 
• Date of last contact**
 
• Date of migration
 
• Date when child reaches 5 years
 

D3 → D3 + 2Y	Third or virtual vaccination*	
 
• Two years after third dose
 
• Date of death
 
• Date of last contact**
 
• Date of migration
 
• Date when child reaches 5 years
 

D1 → D4 + 2Y	First dose or virtual vaccination*	
 
• Two years after virtual fourth dose
 
• Date of death
 
• Date of last contact**
 
• Date of migration
 
• Date when child reaches 5 years
 

D3 → D4 + 2Y	Third dose or virtual vaccination*	
 
• Two years after virtual fourth dose
 
• Date of death
 
• Date of last contact**
 
• Date of migration
 
• Date when child reaches 5 years
 

\* Virtual vaccination: for 5-17 month study group or unvaccinated children

\*\* Date of last contact: lost-to follow-up

The prevalence rate for anaemia will be computed by dividing the number of all cases by the number of enrolled children.

**Table 4 Incidence rate and prevalence calculations for other secondary objectives (children enrolled in active surveillance)**

Endpoints	Numerator	Denominator

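### The deviance-near-1 rule for the Poisson models is uncalibrated for sparse child-level counts and resets itself after scaling; the effect on intervals is confined to the repeat-episode malaria models

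*SAP*

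**What the plan says.** SAP 7.5.1.2 fits a Poisson model with a log person-time offset and reports Wald intervals: "The risk ratio will be derived as the exponential of the coefficient associated with the covariate status and its 95% Wald CI". Its adequacy test is "If the scaled deviance is closed to one, the regression model is adequate. Otherwise, the validity of the model is questionable", followed by "In particular, value greater than 1 indicates overdispersion". Protocol 9.7.9 has the same rule: "If the scaled deviance is closed to one, the regression model is adequate".

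If overdispersion is found, a dispersion parameter is introduced: "This will be done by adding the option DSSCALE and examining the fit statistics" (the option is read here as GENMOD's deviance scale, DSCALE). If the problem persists, a negative binomial model is to be discussed; no number triggers it. The same paragraph asks for a check of the Poisson assumption and of excess zeros, without a criterion.

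For the malaria endpoints, SAP 6.11.2 counts repeats: "If a subject had several cases during the period defined, all episodes will be reported". It then plans these models for any, severe and cerebral malaria, and SAP Table 5 also marks the *P. falciparum* versions. The only random effect, in SAP 7.5.2, is for site. No robust variance or child-level term is planned.

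**The concern.** Deviance/df is expected to be near 1 only when the counts per record are large enough. SAP 7.5.3.4 fits models from 10 cases upward, with covariates measured on each child at entry, in about 20,000 children (Protocol 9.7). Most records are then zero, and the statistic mainly reflects the mean count rather than the dispersion.

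Three faults follow:

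- A correct sparse model fails the closeness test.
- Real between-child heterogeneity in malaria episodes can pass unseen.
- Once the deviance scale is applied, the re-check on the same statistic can no longer show a problem.

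At stake are the Wald intervals for malaria risk factors and the univariate 20% p-value screen in SAP 7.5.3.4, which rely on the same variance.

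**Working it through.** The plan gives no dispersion or coverage figure for these models, so there is none to reproduce.

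**Inputs from the documents**
- Severe malaria: 158 cases in 2,974 Phase III control children over 20 months (Protocol Table 2). Per year: 158/2974 × 12/20 = 0.032. Over 44 months: 158/2974 × 44/20 = 0.117.
- Cerebral malaria: (5 + 1 with anaemia)/2974 = 0.002 over 20 months.
- Smallest model: 10 events in 20,000 children = 0.0005.
- Windows: one year from dose 3 is primary, and the longest analysis runs to Month 44 (SAP 6.11.1).

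**Assumptions not in the documents**
- One record per child.
- Gamma-Poisson heterogeneity with variance μ + kμ², k from 0 to 5.
- Any-malaria means of 0.3 and 1 episode per child.

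**Formulas** (mean μ per child, many children)
- Expected deviance/df: d = 2·E[Y·ln(Y/μ)].
- Expected Pearson/df (variance/mean): 1 + kμ.
- Coverage of a nominal 95% Wald interval for a null covariate: 2Φ(1.96/√(1+kμ)) − 1 if the rule does not fire (d ≤ 1), and 2Φ(1.96·√(d/(1+kμ))) − 1 if it does.

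**Worked case, μ = 0.117.** With correct Poisson data, the terms for Y = 1, 2, 3 are 0.447 + 0.069 + 0.005, so d = 0.521. With k = 5, d is only 0.593, although variance/mean is 1 + 5 × 0.117 = 1.585. The standard error is short by a factor √1.585 = 1.259, and coverage is 2Φ(1.96/1.259) − 1 = 88.0%.

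| Setting | μ | k | d | 1+kμ | Coverage under the SAP rule |
|---|---|---|---|---|---|
| 10 events in 20,000 | 0.0005 | 0 | 0.008 | 1.00 | 95.0% |
| Cerebral malaria | 0.002 | 0 | 0.025 | 1.00 | 95.0% |
| | | 5 | 0.025 | 1.01 | 94.9% |
| Severe, 1 year | 0.032 | 0 | 0.222 | 1.00 | 95.0% |
| | | 2 | 0.224 | 1.06 | 94.3% |
| | | 5 | 0.228 | 1.16 | 93.1% |
| Severe, 44 months | 0.117 | 0 | 0.521 | 1.00 | 95.0% |
| | | 2 | 0.553 | 1.23 | 92.2% |
| | | 5 | 0.593 | 1.58 | 88.0% |
| Any malaria | 0.3 | 0 | 0.840 | 1.00 | 95.0% |
| | | 1 | 0.934 | 1.30 | 91.4% |
| | | 2 | 1.013 | 1.60 | 88.1% |
| Any malaria | 1 | 0 | 1.147 | 1.00 | 96.4% |
| | | 1 | 1.786 | 2.00 | 93.6% |
| | | 2 | 2.250 | 3.00 | 91.0% |

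**Simulation.** The SAP model was fitted to 400 data sets per scenario (10,000 children, three sites, age, unequal follow-up; Monte Carlo error about 1 point).
- The rule fired in 0% of severe-malaria data sets (k up to 2).
- At 0.3 episodes per child, coverage was about 90% (k = 1) and 87% (k = 2), with the rule firing in 0% and 2%.
- At 1 per child it fired every time and raised coverage from 81% to 92% (k = 1) and from 72% to 88% (k = 2).
- It also fired every time on correct Poisson data at these higher means (deviance/df 1.08 to 1.12).
- With Pearson/df as the scale, coverage was 91% to 96% in all scenarios.

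**After scaling.** The scale is φ = deviance/df, so scaled deviance/df = φ/φ = 1 whatever the data. Scaled Pearson/df is not forced to 1: at μ = 1, k = 2 it is 3.00/2.25 = 1.33.

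**Screening.** At k = 2, the 20% screen admits a null covariate with probability 2[1 − Φ(1.2816/√1.234)] = 25% at μ = 0.117, and 2[1 − Φ(1.2816·√(1.013/1.6))] = 31% at μ = 0.3.

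**The case against.** A reader might infer that all intervals from these models are too narrow. The documents do not support that.

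- **Safety endpoints.** For AESI and meningitis, follow-up stops at the first occurrence after each dose (SAP 6.9.3.2), and death occurs once, so there is little or no repeat-event overdispersion. The questionable label on a sparse model changes nothing, because the corrective step is tied to values above 1.
- **Co-primary results.** These are incidence rates with exact Poisson intervals, which this rule does not touch. The models serve a secondary objective of describing risk factors.
- **Very sparse malaria endpoints.** Cerebral malaria and severe malaria over one year lose at most about 2 points for k up to 5. A much larger loss appears if variance/mean is set to 2 at means of 0.03 to 0.10, but that needs k = (2 − 1)/0.03 = 33 down to (2 − 1)/0.10 = 10, and nothing in the documents suggests such values.
- **Frequent malaria.** At about one episode per child the rule fires, and deviance scaling recovers much of the coverage.
- **Episode merging.** SAP 7.2.8.2 combines same-species malaria episodes up to 14 days apart, which removes one source of within-child clustering.

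It would also be too strong to say that the negative binomial step can never be reached. The excess-zeros check, or a look at Pearson/df among the fit statistics, could still prompt it, but no criterion requires this. Finally, data aggregated by covariate pattern would make the deviance more informative. The SAP does not state the unit; the child is only the likelier reading.

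These points limit the consequence. They do not repair the rule.

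**Conclusion.** The concern holds in limited form and should be fixed. On the inferred unit of one record per child, the stated benchmark is wrong for sparse counts whatever the heterogeneity, and the re-check of scaled deviance after deviance scaling is uninformative by construction.

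The cost to the intervals lies in malaria models with roughly 0.1 or more episodes per child and real between-child heterogeneity. Coverage is about 92% (k = 2) to 88% (k = 5) for severe malaria over 44 months, and about 91% (k = 1) to 87–88% (k = 2) for any malaria at 0.3 per child. At one episode per child it is still only 88–94% after scaling (k = 1 to 2). The severe and cerebral means are borrowed from the Phase III control group; k and the any-malaria rate are assumptions.

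**What to change.** In SAP 7.5.1.2:

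1. Delete the deviance-close-to-1 rule and the re-check after deviance scaling.
2. State that the model uses one record per child.
3. Judge dispersion by Pearson chi-square/df.
4. For any, *P. falciparum*, severe and cerebral malaria, use child-level robust (sandwich) variance (a REPEATED statement in GENMOD with the child as subject), or a negative binomial model when Pearson/df exceeds a value stated in advance.

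The AESI, meningitis and death models do not need the robust variance for this reason. Record the departure from Protocol 9.7.9 in SAP section 9. The cost is SAP wording and one code statement; some malaria intervals become slightly wider.

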### **7.5.2. Random effect poisson regression model**

As sensitive analysis Mixed-Poisson model including study site as random-effect will be conducted using the SAS GLIMMIX procedure.

```
PROC GLIMMIX data=<filename> ;  
  CLASS X Z;  
  MODEL Y= X / OFFSET=Ln_PY DIST=poisson LINK=log ;  
  RANDOM Z;  
  RUN;
```

### **7.5.3. Covariates**

#### **7.5.3.1. Potential confounding variables**

Patient characteristics and potential confounding variables will be based on the *first home visit or first hospitalisation*.

The category of covariates will be presented in the TFLs template part.

##### **7.5.3.1.1. Individual level covariates**

For all enrolled study participants:

- **General covariates:**
  - Demographic parameters:
    - Age
    - Gender
    - Study site
    - Household configuration
    - Neighbourhood of residence
  - Medical history:
    - Signs and symptoms
    - Developmental delay or physical disabilities, known pre-existing conditions and risk factors

- Health behaviour:
  - Usual health care seeking place
  - Distance to the usual health care provider
- **Malaria related covariates:** Malaria preventive measures
  - use of bednets,
  - indoor residual spraying,
  - seasonal malaria chemoprevention
- **Comorbidity**
  - known haemoglobinopathies,
  - known HIV infection

### 7.5.3.2. **Forced-in covariates**

As described in section 7.5.1, some clinical covariates will be forced-in multivariable models related to safety endpoints and related to impact endpoints.

#### 7.5.3.2.1. **Forced-in covariates for safety endpoints**

- Demographic parameters:
  - Age
  - Gender
  - Study site
- Health behaviour:
  - Usual health care seeking place
  - Distance to the usual health care provider

*Other forced-in covariates may be included at the time of the final analysis.*

#### 7.5.3.2.2. **Forced-in covariates for other secondary endpoints**

The same covariates as for safety endpoints.

*Other forced-in covariates may be included at the time of the final analysis.*

### 7.5.3.3. **Summary**

The following table summarises the models and covariates used for each endpoint.

**Table 6 Covariates used in the models according to each endpoint**

Endpoint	Population	Model	Forced-In covariates	Individual level covariates		
				General covariates	Comorbidity	Malaria specific covariates
AESI	AS ATP	Fixed effect Poisson models	o	o	o	
Meningitis	AS ATP	Fixed effect Poisson models	o	o	o	
Cerebral malaria	AS ATP	Fixed effect Poisson models	o	o	o	
Malaria	AS ATP	Fixed effect Poisson models	o	o	o	o
Deaths (All causes)	AS ATP	Fixed effect Poisson models	o	o	o	o

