Malaria attributed hospitalisations	# of children hospitalised during study period where malaria is listed as the primary diagnosis Source: Hospitalisations	Person-years contribution of enrolled children

Incidence rates will be adjusted by means of Poisson regression models (the dependent variable will be the number of events). The details are given in Section 9.7.9.

Univariate and multivariable models will be conducted. Those adjusted covariates are described in Section 9.3.3:

- Study site.
- Demographic parameters such as age at reference date.

CONFIDENTIAL115055 (EPI-MALARIA-002 VS AME)
Protocol Amendment 7 Final

- Medical history and other risk factors such as chronic disease or diagnosed congenital disease, known HIV infection, malaria, malnutrition, drugs exposure, toxic agent exposure.
- Use of malaria control measures such as bednets, indoor residual spraying, seasonal malaria chemoprevention.
- Comorbidity factors such as premature birth, history of trauma.
- Health care seeking behaviour and distance to health care facilities.
- Type of health care facility.
- Neighbourhood of residence (urban/rural area).
- Total number of outpatient visits per centre.
- Seasonal MTI (i.e. parasite prevalence) estimated in study EPI-MAL-005 on the vaccine ineligible group (see [Annex 3](#) for definition).
- Other centre level covariates estimated in study EPI-MAL-005 per year: malaria control intervention use, bednet use and health care seeking behaviour.

The same strategy as described in Section [9.7.6.2](#) will be used for covariates selection to be included in the multivariable model.

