All cause hospitalisation	# of children hospitalised during the follow-up time of each analysis Source: Hospitalisations	Person-years contribution of enrolled children during the follow-up time of each analysis
Malaria attributable hospitalisation	# of children hospitalised during the follow-up time of each analysis where malaria is listed as the primary diagnosis Source: Hospitalisations	Person-years contribution of enrolled children during the follow-up time of each analysis
P. falciparum Malaria attributable hospitalisation	# of children hospitalised during the follow-up time of each analysis where P. falciparum malaria is listed as the primary diagnosis Source: Hospitalisations	Person-years contribution of enrolled children during the follow-up time of each analysis
Anaemia in hospitalised children	# cases of anaemia Source: Hospitalisations	Number of enrolled children
Severe anaemia in hospitalised children	# cases of severe anaemia Source: Hospitalisations	Number of enrolled children

As done for safety endpoints, analysis of risk factors will be conducted by means of univariate and multivariable Poisson regression models for ***any malaria, severe malaria and cerebral malaria***. The methods are described in Section 7.5.1. The covariates and their select method are described in Section 7.5.3.

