**7.5.3.4. Strategy for covariates selection**

For multivariable Poisson models, the following strategy for covariates selection will be applied.

The model will include time-independent covariates at study entry from EPI-MAL-002.

The covariates are described in section [7.5.3.1](#).

Covariates occurring in less than 5% of the subjects (percentage will be computed over subjects both in 6-12 weeks and 5-17 months group) will not be included in the model. Of note, models will be run if a minimum number of cases of each endpoint are observed (at least 10 cases in total).

The predefined clinically relevant covariates described in section [7.5.3.2](#) will be forced into the models.

Covariates selection will be done using statistical significance. Confounders will be included in the multivariable models if univariate p-value will be less than 20%.

Co-linearity (i.e. correlation among predictor covariates) will be assessed on the full model including forced-in covariate and the other selected with the variance inflation factor (cutoff level = 10). The method is described in the following section [7.5.3.5](#).

Then the selected set of covariates will be entered in the final model without transformations and the full model will be presented.

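### SAP Table 6 gives cerebral malaria no malaria-prevention covariates: an undeclared departure from protocol 9.7.7.2 for one of its two models, and unexplained for the other

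*SAP*

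**What the plan says.** SAP 7.5.3.3 relies on Table 6, headed "Covariates used in the models according to each endpoint". The cerebral malaria row reads "Cerebral malaria AS ATP Fixed effect Poisson models o o o": marked for forced-in, general and comorbidity covariates. The malaria row reads "Malaria AS ATP Fixed effect Poisson models o o o o"; the fourth mark is the malaria-specific column. All-cause death also has four marks; AESI and meningitis have three.

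SAP 7.5.3.1.1 defines the malaria-specific group as "Malaria preventive measures": bednets, spraying and seasonal chemoprevention, listed for all enrolled participants. None of them is a named forced-in covariate (those are age, gender, site, usual place of care and distance to it), although SAP 7.5.3.2.1 adds: "Other forced-in covariates may be included at the time of the final analysis".

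The SAP models risk factors for cerebral malaria twice. Section 6.10.4 lists it with each AESI, aetiology-confirmed meningitis and death. Section 6.11.2 says: "As done for safety endpoints, analysis of risk factors will be conducted by means of univariate and multivariable Poisson regression models for" any, severe and cerebral malaria, and refers to 7.5.3 for the covariates.

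Protocol 9.7.7.2 includes cerebral malaria in its Table 8, plans Poisson adjustment of those rates, and names among the covariates: "Use of malaria control measures such as bednets, indoor residual spraying, seasonal malaria chemoprevention". It makes no exception for cerebral malaria. Protocol 9.7.6.2, the safety section, plans risk-factor models for AESI and meningitis only, and its covariate list has no malaria control measures.

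**The concern.** Cerebral malaria is severe P. falciparum malaria with impaired consciousness (SAP 7.2.9.4), so the plan offers prevention measures to the parent endpoint and withholds them from its subset. Describing risk factors for malaria is a stated secondary objective, and protocol 7.2 records cerebral malaria as an important potential risk in the risk management plan. Without these covariates, the analysis cannot say whether a child's own use of nets, spraying or chemoprevention is associated with cerebral malaria. Covariates that vary with such use inside a site, such as distance or place of care, may carry part of its effect. Their rate ratios would also not be comparable with those from the severe malaria model.

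**Working it through.** The plan states no figure on this point, so the check is mainly a comparison of texts, followed by two small calculations.

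**1. The 6.11.2 model.** Protocol 9.7.7.2 covers cerebral malaria and lists the control measures. SAP 6.11.2 keeps the model and takes its covariates from 7.5.3, where the only row named cerebral malaria omits them. SAP Section 9 withdraws only the aggregated variables from EPI-MAL-005; the individual measures are not mentioned. On the plain reading this is an undeclared departure.

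**2. The 6.10.4 model.** Protocol 9.7.6.2 lists no control measures, so the blank does not contradict it. But all-cause death is also a 6.10.4 endpoint. SAP Table 5 gives it no risk-factor model under the other secondary objectives, yet Table 6 marks it for the malaria-specific covariates. So a rule that safety models omit these covariates does not explain the blank. Protocol 9.9 also says that the introduction of control measures has to be taken into account when safety and malaria data are analysed.

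**3. Will the model be run?** SAP 7.5.3.4 requires at least 10 cases. The only rate in the documents is from the Phase III controls (protocol 7.2): 5 cerebral cases, or 6 counting the one with anaemia, in 2974 children over 20 months. That case definition differs from the present one, so the rate is an assumption.
- Person-years: 2974 × 20/12 = 4956.7. Rate: 5/4956.7 to 6/4956.7 = 101 to 121 per 100,000.
- One year from dose 3, 20,000 children, about 20,000 person-years: 20 to 24 cases; Poisson probability of at least 10 cases above 0.99.
- 12-month risk period over four doses: 10,000 × (1/12 + 1/12 + 1 + 1) = 21,666.67 person-years per group, which reproduces protocol Table 6. Two groups give 43,333 person-years and 44 to 52 cases.
- At half the rate: 10 to 12 and 22 to 26 cases. At a quarter: 5 to 6 and 11 to 13.

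The model will probably be run unless the rate is well below Phase III. If it were fitted separately in the two age groups, the full-rate counts would halve.

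**4. Illustration for site.** Assume that nets halve cerebral malaria and that use is 80% in one site and 50% in another. With no true site difference, the site rate ratio is (1 − 0.5 × 0.8)/(1 − 0.5 × 0.5) = 0.60/0.75 = 0.80. With half that net effect (25%) it is (1 − 0.25 × 0.8)/(1 − 0.25 × 0.5) = 0.80/0.875 = 0.91. With equal use it is 1.00. The documents give neither net use nor net effect.

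**The case against.** The best defence is that Table 6 is compressed. It has no row for severe or P. falciparum malaria, so its malaria row must be an umbrella, and protocol 9.2.5.5 defines any malaria to include cerebral malaria. SAP Table 5 groups all the malaria endpoints together and gives only cerebral malaria two risk-factor analyses. The separate cerebral row could therefore serve the 6.10.4 model alone, with the malaria row serving 6.11.2. On that reading nothing departs from the protocol. The reading is possible, but the table does not state it, and a programmer would follow the row that bears the endpoint's name. The marks for all-cause death also show that the table does not divide cleanly between safety and malaria models.

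A second defence is parsimony. The forced-in set already uses at least 6 parameters (age 1, gender 1, three sites 2, place of care 1, distance 1). With 20 to 24 cases that is about 3 to 4 cases per parameter. A lean model is defensible, but the SAP does not give this as its reason.

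Third, the clause allowing further forced-in covariates leaves room for the measures. It does not commit to them, and the decision would fall at the final analysis.

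**Conclusion.** The point holds and should be corrected. It rests on reading the explicit cerebral malaria row as governing both models, and on the table columns having been extracted correctly.

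Four stronger conclusions that a reader might draw are not supported:
- That the blank breaches the protocol for both models. It does so only for 6.11.2; protocol 9.7.6.2 asks for no control measures.
- That the protocol guarantees adjustment. The measures would only be candidates: "Confounders will be included in the multivariable models if univariate p-value will be less than 20" per cent (SAP 7.5.3.4), and anything occurring in under 5% of subjects is dropped. What is lost is the chance to enter.
- That the 0.80 carries over to other covariates. Site is a forced-in fixed effect and takes up between-site differences in use. Only within-site correlation can bias distance or place of care, and the documents give no data to size it.
- That the incidence results are affected. Crude cerebral malaria rates and their intervals do not depend on Table 6.

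**What to change.** In SAP Table 6, mark the malaria-specific column for cerebral malaria. Add a footnote that the row applies to the 6.11.2 model and also to the 6.10.4 model. Keep the three measures as candidates under the existing 5%, 20% and 10-case rules. If the blank is intended, declare and justify it in SAP Section 9 and say which row governs each model.

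The cost is one mark and one footnote. The data are already recorded at home visits and hospitalisations, and SAP 7.5.3.1 takes covariate values from the first of these, so nothing new is collected. The statistical price is a thinner model. If all three measures entered as binary terms, the 6 parameters would become 9. With 20 to 24 cases, that is 20/9 = 2.2 to 24/9 = 2.7 cases per parameter, so the intervals would be wide and should be reported as such.
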